#### Exploratory objectives

- To develop an integral pharmacokinetic/pharmacodynamic (PK/PD) model describing the relationship between TB31F dose, time, individual characteristics, serum TB31F concentrations and SMFA and DSF/DMFA
- To assess the transmission-blocking activity of participant serum after TB31F administration as assessed in the Standard Membrane Feeding Assay (SMFA) at each dose level in Malian individuals
- To assess the quantitative relationship between SMFA, DSF, and DMFA results
- To assess the IC80 serum concentration after TB31F administration resulting in 80% transmission-blocking activity (TBA) in naturally *P. falciparum* infected individuals
- To assess the IC80 serum concentration after TB31F administration resulting in 80% transmission-reducing activity (TRA) in naturally *P. falciparum* infected individuals
- To assess the impact of naturally acquired TRA, present prior to TB31F administration, on transmission endpoints and TB31F efficacy estimates
- To assess human and parasite genomic variation and association with parasite measures
- To assess the impact of plasma biomarkers on malaria transmission efficiency

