## Method

### Study design

The study is designed as a Phase 1/2a single-centre, double-blind, dose escalation, age de-escalation trial in malaria-exposed Malian adults and children. Two sequential stages of clinical research are conducted, each recruiting a distinct cohort of participants to confirm: 1. TB31F safety and 2. TB31F efficacy. Pharmacokinetic measurements will be performed in both safety and efficacy cohorts.

In total, a minimum of 165 participants will be recruited and enrolled; 45 adults and 30 children for the safety study, and ≥ 90 adults and children for the efficacy study. In the tables below, the cohorts are described with the number of participants, the duration of follow-up and the dose of TB31F administered.

*Table 1. Study design for Cohort 1 (Adults): Safety and pharmacokinetics (18-50 years of age)*

Group	Dose	N	Volume TB31F/Saline	Sample timepoints*	Safety follow-up after each dose administration
1	1A: Control (normal saline)	5	0.2 mL	Day 0 (Baseline), 1, 5, 7, 14, 21, 28, 42, 56, 84	Solicited local and systemic AEs (days 1-7); Unsolicited AEs (study duration); SAEs (study duration)
	1B: 10 mg mAb TB31F	10			
2	2A: Control (normal saline)	5	2 mL		
	2B: 100 mg mAb TB31F	10			
3	3A: Control (normal saline)	5	4 mL		
	3B: 200 mg mAb TB31F	10			

\* Group 1 participants will be followed-up until day 28

*Table 2. Study design for Cohort 1 (Children): Safety and pharmacokinetics in school age children (>10-15 years)*

Group	Dose	N	Volume TB31F/Saline	Sample timepoints	Safety follow-up after each dose administration
4	4A: Control (normal saline)	5	0.2 mL	Day 0 (Baseline), 1, 5, 7, 14, 21, 28, 42, 56, 84	Solicited local and systemic AEs (days 1-7); Unsolicited AEs (study duration); SAEs (study duration)
	4B: 10 mg mAb TB31F	10			
5	5A: Control (normal saline)	5	2.0 mL		
	5B: 100 mg mAb TB31F	10			

*Table 3. Study design for Cohort 2: Efficacy in a mixed age cohort (>10-50 years of age)*

Group	Dose	N	Volume TB31F/Saline	Sample timepoints	Safety follow-up after each dose administration
6.1	6AB: Control (normal saline)	15	0.6* mL	Day 0 (Baseline), 1, 5, 14, 21, 28, 56, 84	Solicited local and systemic AEs (days 1-7); Unsolicited AEs (study duration); SAEs (study duration)
	6B: 30 mg mAb TB31F	30	0.6* mL		
6.2	6AC: Control (normal saline)	15	2.0 mL		
	6C: 100 mg mAb TB31F	30	2.0 mL		

AE = Adverse events, SAE = Serious adverse events. Participants will be randomised in a 1:2:1:2 ratio to the 6AB, 6B, 6AC, or 6C group.

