#### Efficacy outcome measures related to mosquito infection prevalence (oocyst prevalence):

11. Mosquito infection prevalence, assessed by DSF and measured as the proportion dissected with any number of oocysts, compared within groups between baseline and all feeding timepoints, and between groups at all feeding timepoints (timeframe: day 0 [baseline], 1, and 5)
12. Mosquito infection prevalence, assessed by DMFA and measured as the proportion dissected with any number of oocysts, compared within groups between baseline and all feeding

timepoints, and between groups at all feeding timepoints (timeframe: day 0 [baseline], 1, 5, and 14)

13. The association between naturally acquired anti-gametocyte immune responses and naturally acquired functional TRA on mosquito infection prevalence.

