**Efficacy outcome measures related to participant infectivity:**

17. Participant infection prevalence, assessed by DSF as the proportion of individuals infectious to any number of mosquitoes, compared within groups between baseline and all feeding timepoints, and between groups at all feeding timepoints (timeframe: day 0 [baseline], 1, and 5)

18. Participant infection prevalence, assessed by DMFA as the proportion of individuals infectious to any number of mosquitoes, compared within groups between baseline and all feeding timepoints, and between groups at all feeding timepoints (timeframe: day 0 [baseline], 1, 5, and 14)

19. The association between naturally acquired anti-gametocyte immune responses and naturally acquired functional TRA on participant infectivity.

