### Analysis approach:

- For all ELISA samples, TB31F antibody density and prevalence will be determined by ELISA. All samples will be processed in duplicate alongside blank wells (for background correction), a standard curve (for concentration interpolation), and non-treated local controls (for seropositivity calculation). Optical density values from duplicate observations will be compared using the coefficient of variation (CV) and will be re-run if the CV exceeds 30%. OD values in agreement will be converted to concentrations using ADAMSEL software based on plate specific control wells; the mean of duplicate concentration estimates will be used for analyses. Antibody density will be expressed in  $\mu\text{g/mL}$ .
- Seropositivity will be calculated using either a) the pooled concentration values of non-treated local controls (including trial specific controls), defined as the mean of these values plus 2 standard deviations, or b) using a two-normal compartmental mixture model, using all values from the control and treated samples, in which the mean of the lower normally distributed population of values plus 2 SD defines the threshold for positivity.

- TB31F antibody density will be plotted over time per individual and either as a mean or geometric mean per group. Mixed effects models may be used to investigate the interaction of timepoints and group on TB31F antibody concentration, allowing for participant specific random intercepts to control for the correlation within individuals.
- TB31F pharmacokinetics will be analyzed using standard non-compartmental methods to establish the maximum concentration ( $C_{max}$ ), terminal half-life ( $t_{1/2}$ ), area under the curve (AUC  $0-\infty$ ) and Volume of Distribution ( $V_d$ ) for each participant who received mAb TB31F. Additionally, the absorption rate constant ( $K_a$ ) will be determined. Geometric mean and geometric coefficients of variation of  $T_{1/2}$  and  $V_d$ , as well as of dose-adjusted  $C_{max}$  and AUC will be reported per dose group and overall.

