### Efficacy outcome measures

#### **Efficacy outcome measures related to within-group % reduction in proportion infected mosquitoes:**

We will determine averaged within-individual percent reduction in the proportion of mosquitoes infected at days post-treatment (1, 5, 14) compared to baseline (day 0) for each group. This will be assessed through DMFA and DSF and outcomes for these different feeding assays will be presented separately as percentage reduction (with 100% as total reduction of transmission, and negative values as enhanced transmission) with 95% confidence interval. Data will be analysed for all individuals who received the product per protocol and only for those individuals who are infectious at baseline (i.e. infecting at least one mosquito with any number of oocysts). All analyses on within-individual percentage reduction in the proportion of infected mosquitoes will use a mixed effects generalized linear model assuming a binomial error structure and a log-link, using individual mosquito data with day of follow-up and dose of TB31F and their interaction as fixed effects. A random intercept will be added to models to allow for participant-level variation in pre-intervention transmissibility and thus account for the correlation between outcomes for mosquito samples from the same participant (i.e. intra-cluster correlation).

In exploratory analyses, these analyses will be performed following stratification for naturally acquired transmission reducing immunity, as quantified by SMFA at baseline (pre-TB31F administration) samples.

The impact of naturally acquired transmission reducing immunity, assessed in baseline samples by SMFA (TRA>50%; TRA>80%) and by antibody prevalence to known gamete antigens Pfs230 and Pfs48/45, on infecting mosquitoes will also be determined. For this, TRA as categorical variable and antibody prevalence (binary variable), will be added as fixed effects to mixed effects logistic regression models on proportion infected mosquitoes at baseline (pre-TB31F administration). These models may be expanded to include human genetic factors (e.g. a fixed effect for HbAS or HbAC carriage as compared to wild-type HbAA).

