#### **Efficacy outcome measures related to mosquito infection prevalence (oocyst prevalence):**

In this analysis, we do not assess reductions in infection rates but present the average prevalence of infected mosquitoes (percentage of mosquitoes with any oocyst density) at each timepoint for each arm. Data will be presented for DMFA and DSF separately.

If, despite randomization, there are considerable differences in baseline infectivity, we may adjust for baseline infectivity. We will fit a mixed effects logistic regression with fixed factors time and study arm and their interaction and individual-specific random intercepts to estimate proportions (or adjusted proportions) at each timepoint for each arm and compare prevalence estimates between time-points for each arm and between arms for each time-point using odds ratios (and 95% CIs).

In exploratory analyses, these analyses will be performed following stratification for naturally acquired transmission reducing immunity, as quantified by SMFA at baseline (pre-TB31F administration) samples.

The impact of naturally acquired transmission reducing immunity, assessed in baseline samples by SMFA (TRA>50%; TRA>80%) and by antibody prevalence to known gametocyte antigens Pfs230 and Pfs48/45, on oocyst prevalence will also be determined. For this, TRA as categorical variable and antibody prevalence (binary variable), will be added as fixed effects to mixed effects logistic regression models on mosquito infection prevalence at baseline (pre-TB31F administration). These models may be expanded to include human genetic factors (e.g. a fixed effect for HbAS or HbAC carriage as compared to wild-type HbAA).

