#### **Efficacy outcome measures related to participant infectivity:**

The prevalence of infectiousness (i.e. the proportion of individuals infecting at least one mosquito) will be presented per arm and timepoint and presented for DMFA and DSF separately. We will fit a logistic regression with fixed factors time and study arm and their interaction to estimate proportions (or adjusted proportions if baseline proportions differ quite significantly between arms) at each timepoint for each arm and compare prevalence estimates between time-points for each arm and between arms for each time-point using odds ratios (and 95% CIs).

Similar to the paragraph on oocyst prevalence, naturally acquired transmission reducing immunity and human genetic factors may be added as fixed effect in logistic regression models on participant infectivity as binary dependent variable.

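### Natural antibody to Pfs230 and Pfs48/45 enters the outcome 13 models only as yes/no, with no stated cut-off and no planned analysis of the level

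*SAP*

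**What the plan says.** Outcome 13 (Study Outcome Measures, mosquito infection prevalence) is worded in terms of immune responses, not seropositivity: "The association between naturally acquired anti-gametocyte immune responses and naturally acquired functional TRA on mosquito infection prevalence".

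Under Efficacy outcome measures, the analysis text on within-group percentage reduction and the text on oocyst prevalence each set out the model for this question. Both use the same coding: "For this, TRA as categorical variable and antibody prevalence (binary variable), will be added as fixed effects to mixed effects logistic regression models". The oocyst prevalence text names the measurement: "by antibody prevalence to known gametocyte antigens Pfs230 and Pfs48/45, on oocyst prevalence will also be determined". Both models use baseline data, before TB31F is given.

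For outcome 19, the text on participant infectivity is looser. It refers back to the oocyst prevalence paragraph and says "naturally acquired transmission reducing immunity and human genetic factors may be added as fixed effect in logistic regression models on participant infectivity". The terms are optional there, and no coding is named.

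The related Cohort 2 objective is listed as exploratory: "To assess the impact of naturally acquired TRA, present prior to TB31F administration, on transmission endpoints and TB31F efficacy estimates".

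The SAP states no cut-off, expected seroprevalence, effect size or power for natural antibody to either antigen.

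**The concern.** A seropositivity call is normally a cut made on a quantitative reading. Entering only the call treats everyone above the cut as alike, and everyone below it as alike. If infectivity falls gradually as antibody rises, the model cannot use the differences within each group, and a real association is more likely to be missed.

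The SAP gives no reason for the cut, and it handles TB31F differently. Under estimated inhibitory concentrations, TB31F activity is modelled as a graded function of serum concentration, on the square-root scale. The natural response gets no graded analysis.

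The binary variable is also undefined. With no cut-off stated for natural antibodies, the analyst chooses it later, and the result depends on that choice. At stake is the reading of an exploratory result: a null finding from a weak coding could be taken as evidence that natural anti-gametocyte antibody has little bearing on transmission.

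**Working it through.** **The plan's own figure.** None exists for outcome 13. The 97% under Sample size concerns the efficacy comparison (90% true reduction tested against 80%) and has no bearing here.

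**Inputs from the SAP.** Cohort 2 size: "≥ 90 adults and children for the efficacy study" (Study design). From Sample size: 40 mosquitoes per participant and timepoint, 15% infected at baseline, intra-cluster correlation 0.5. From Confidence intervals and P values: significance level 0.05.

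**Assumptions, not in the SAP.** Two-sided test; log antibody level normally distributed; effect linear in log level; an effect large enough to give the level analysis 80% or 90% power; seroprevalence between 10% and 90%.

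**Step 1: information kept by a cut.** Let p be the proportion seropositive and c = z(1-p). Cutting a normal exposure at c multiplies the expected test statistic by r = φ(c)/√(p(1-p)), and the information kept is r².

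- p = 50%: r = 0.3989/0.5 = 0.798, r² = 0.637
- p = 20% or 80%: r = 0.2800/0.4 = 0.700, r² = 0.490
- p = 10% or 90%: r = 0.1755/0.3 = 0.585, r² = 0.342

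**Step 2: power.** Yes/no power = Φ(r × (1.960 + z_power) − 1.960).

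Level analysis at 80% power, expected statistic 1.960 + 0.842 = 2.802:

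- p = 50%: Φ(2.236 − 1.960) = 61%, a loss of 19 points
- p = 20% or 80%: Φ(1.961 − 1.960) = 50%, a loss of 30 points
- p = 10% or 90%: Φ(1.639 − 1.960) = 37%, a loss of 43 points

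Level analysis at 90% power, expected statistic 1.960 + 1.282 = 3.242:

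- p = 50%: 73%, a loss of 17 points
- p = 20% or 80%: 62%, a loss of 28 points
- p = 10% or 90%: 47.5%, a loss of 42.5 points

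This gives the range of 17 to 43 points.

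**Step 3: simulation with the SAP's inputs.** The set-up was 90 participants, 40 mosquitoes each, 15% infected for the average participant and a correlation of 0.5 on the logit scale. The model was a random-intercept logistic regression with a likelihood-ratio test at 0.05, over 250 data sets. Simulation error is at most √(0.5 × 0.5/250), about 3 points. With an assumed log odds ratio of 0.6 per SD, power was 84% with the level. With the yes/no term it was 63%, 51% and 46% at 50%, 80% and 10% seropositive: losses of 21, 33 and 38 points, in line with step 2.

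**Step 4: when the assumptions fail.**

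- *Bimodal levels.* Take two normal groups 3 to 4 SD apart, 20-80% in the upper group, the cut at the lower mean plus 2 SD, and the effect still linear. The cut keeps 63-81% of the information. Against 80% power for the level, yes/no power is 61-72%, a loss of about 8 to 19 points.
- *A true step at the cut-off.* The order reverses. In simulation (200 data sets) the yes/no term had 82% power against 63% for the level with the step at 50% seroprevalence, and 81% against 60% with the step at 80%.
- *A true step elsewhere.* In the same runs, with the step at 50% but the cut placed at 80% seropositive, yes/no power was 27% against 63% for the level. The yes/no advantage therefore needs a well-placed cut, and the SAP does not place one.

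**The case against.** The strongest reply is that the SAP makes no power claim for this analysis and misstates nothing. The objective is exploratory, and the Purpose section leaves room for exploratory work, naming the choice of cut-points for continuous variables as an example. A level analysis could therefore be added without breaching the plan. Natural immunity is also measured functionally by SMFA in the same models. If variation among seronegatives is only assay background, a yes/no term is defensible, and with a true threshold it is better. All of this stands and keeps the point small. It does not supply the missing level analysis, because both model paragraphs commit to one coding.

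Three stronger readings are tempting, and the document does not support them.

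- *A loss of about 65 points.* This needs only 2-3% of participants to be seropositive. A reader might get there by applying the threshold under Pharmacokinetic outcome measures, "the pooled concentration values of non-treated local controls (including trial specific controls), defined as the mean of these values plus 2 standard deviations", to natural antibodies. That rule is written for the TB31F ELISA, has a mixture-model alternative beside it, and is nowhere extended to natural Pfs230 or Pfs48/45 serology.
- *The same loss for outcome 19.* Outcome 19 asks a parallel question ("The association between naturally acquired anti-gametocyte immune responses and naturally acquired functional TRA on participant infectivity"), but its antibody terms are optional and their coding is only implied by the reference back. It is also a participant-level yes/no outcome, so the range above does not carry over.
- *Residual confounding.* This would matter if the binary term were used for adjustment. The two model paragraphs estimate an association at baseline and state no such use.

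**Conclusion.** The concern holds as a minor point about outcome 13. The SAP fixes a yes/no term for natural antibody to Pfs230 and Pfs48/45, gives no cut-off for it and plans no analysis of the level. Under a graded relation this is the weaker method, by the 17 to 43 points derived above. That range describes what dichotomising does under stated assumptions. It is not a forecast for this trial, because the effect size, the distribution of levels and the seroprevalence are all unknown from the document. Entering the level is the better default: it needs no cut-off, and it is inferior only when the true relation is close to a step at the cut that is used.

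**What to change.** In the two analysis paragraphs (within-group percentage reduction and oocyst prevalence), enter the baseline log antibody level, per SD, for each of Pfs230 and Pfs48/45 as the main term. Add a linearity check such as a quadratic or spline term, which would also help to show a threshold. Keep seropositivity as a secondary presentation, and state its cut-off for natural antibodies. Use the same coding in the participant infectivity paragraph (outcome 19) wherever the optional terms are added.

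The cost is SAP wording only, provided that the natural-antibody assay gives a quantitative reading. The SAP does not describe that assay, so this is an assumption. The small downside is a result per SD of log level, which is less simple to read than positive versus negative.

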#### **Efficacy outcome measures related to mosquito infection prevalence (oocyst prevalence):**

In this analysis, we do not assess reductions in infection rates but present the average prevalence of infected mosquitoes (percentage of mosquitoes with any oocyst density) at each timepoint for each arm. Data will be presented for DMFA and DSF separately.

If, despite randomization, there are considerable differences in baseline infectivity, we may adjust for baseline infectivity. We will fit a mixed effects logistic regression with fixed factors time and study arm and their interaction and individual-specific random intercepts to estimate proportions (or adjusted proportions) at each timepoint for each arm and compare prevalence estimates between time-points for each arm and between arms for each time-point using odds ratios (and 95% CIs).

In exploratory analyses, these analyses will be performed following stratification for naturally acquired transmission reducing immunity, as quantified by SMFA at baseline (pre-TB31F administration) samples.

The impact of naturally acquired transmission reducing immunity, assessed in baseline samples by SMFA (TRA>50%; TRA>80%) and by antibody prevalence to known gametocyte antigens Pfs230 and Pfs48/45, on oocyst prevalence will also be determined. For this, TRA as categorical variable and antibody prevalence (binary variable), will be added as fixed effects to mixed effects logistic regression models on mosquito infection prevalence at baseline (pre-TB31F administration). These models may be expanded to include human genetic factors (e.g. a fixed effect for HbAS or HbAC carriage as compared to wild-type HbAA).

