## Sample size

The sample size is standard for the safety cohorts without formal sample size estimation. Sample size is informed by the anticipated efficacy from an earlier Phase I study and the transmission blocking effects observed in similar Malian cohorts when treated with transmission blocking drugs; this is done for the efficacy cohort only. This sample size for the efficacy cohort (n=30 per group) will give us 97% empirical power to detect >80% reduction in infectivity (defined as the percentage of mosquitoes with at least one oocyst) with a one-tailed test with a 0.025 level of significance when dissecting at least 40 mosquitos per participant at each timepoint. This power calculation is based on an online tool based on mixed effects logistic regression, an expected reduction in infectivity of 90%, an expected baseline proportion of infectivity of 15% for the average participant (accounting for non-infectious participants), and a conservative expected intra-cluster correlation of 0.5. Of note, this includes non-infectious individuals. In the four years that we performed NECTAR studies with a highly similar

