study population, 66.0-79.5% of individuals infected at least one mosquito at enrolment with 14.2-17.0% of mosquitoes becoming infected. The power calculation given above includes all individuals (infectious and non-infectious). If we retain 30 individuals per arm and exclude those individuals who are not infectious at baseline ( $\leq 10$ ), the expected percentage of infected mosquitoes will increase from 15% (in the situation where some individuals infect no mosquitoes) to  $\sim 20\%$ . Based on a mixed effects logistic regression we looked at 200 simulations with an expected reduction in infectivity of 90%, an expected baseline proportion of infectivity of 20% for the average participant, and an expected intra-cluster correlation of 0.4. We estimated 91.5% empirical power to detect  $>80\%$  reduction in infectivity with a one-tailed test with a 0.025 level of significance when including 30 participants (of whom 20 are included in the analysis, i.e. after excluding non-infectious individuals) and dissecting 40 mosquitoes per participant at each timepoint. Importantly, these analyses are based on DMFA where venous blood is offered to mosquitoes. We and others have previously demonstrated that mosquito infection rates are at least 2-fold higher when allowing mosquitoes to feed directly on the skin of participants. When the expected baseline proportion infected mosquitoes is updated to account for higher infection rates by skin feeding (30% for the average participant) and we conservatively increase intra-cluster correlation to 0.8, we estimated 96% empirical power to detect  $>80\%$  reduction in infectivity with a one-tailed test with a 0.025 level of significance when including 30 participants and dissecting 40 mosquitoes per participant.

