#### Statistical Software

- Safety data analysis will be performed in STATA (latest version available), or R.
- SMFA, DMFA and DSF data analysis will be performed in R.
- The pharmacokinetic and pharmacokinetic/pharmacodynamic analyses will be performed by means of compartmental non-linear mixed effects modelling, using the software package NONMEM V7.5 (Icon, Dublin, Ireland) using R and the Perl modules package Perl Speaks NONMEM v5.4.0 for data processing.

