#### **Efficacy outcome measures related to mosquito infection intensity (oocyst density):**

In this analysis, we do not assess reductions in infection intensity but present the average oocyst density at each timepoint for each arm. Data will be presented for DMFA and DSF separately.

We will fit a mixed effects negative binomial regression model with fixed factors time and study arm and their interaction and individual-specific random intercepts to estimate average oocyst densities at each timepoint for each arm and compare prevalence estimates between time-points for each arm and between arms for each time-point using oocyst density ratios (and 95% CIs).

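### The SAP wants the average infection prevalence and oocyst density per arm and day but names only random-intercept models, with no step that averages over participants.

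*SAP*

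**What the plan says.** The section of the SAP on mosquito infection prevalence sets out to "present the average prevalence of infected mosquitoes (percentage of mosquitoes with any oocyst density) at each timepoint for each arm". It then fits a mixed effects logistic regression on time, arm and their interaction, with "individual-specific random intercepts to estimate proportions (or adjusted proportions) at each timepoint for each arm", and compares days and arms by odds ratios.

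The section on mosquito infection intensity has the same form. The aim is to "present the average oocyst density at each timepoint for each arm". The tool is a mixed effects negative binomial regression with "individual-specific random intercepts to estimate average oocyst densities at each timepoint for each arm", and comparisons use density ratios.

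Neither section says how a per-arm, per-day average is to be obtained from the fitted model. No marginal model, generalised estimating equations (GEE) or standardisation is named. Under Statistical Software the SAP says only that "SMFA, DMFA and DSF data analysis will be performed in R".

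On variation between participants, the Sample size section plans on "an expected baseline proportion of infectivity of 15% for the average participant" with "a conservative expected intra-cluster correlation of 0.5". An infectious-only scenario uses 20% and "an expected intra-cluster correlation of 0.4", and a skin-feeding scenario uses 30% and 0.8. The same section reports that in earlier, similar cohorts 66.0 to 79.5% of people infected at least one mosquito and 14.2 to 17.0% of mosquitoes became infected.

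**The concern.** With a logit or log link, the fixed effects of a random-intercept model do not describe the arm average. They describe a participant whose random intercept is zero, which is the median participant if the intercept is normal. When infectivity is low for most people and high for a few, the median lies well below the mean.

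Two analysts could both follow the SAP on the same data. One might back-transform the fixed effects and the other average over participants, and their tables would differ. For these outcomes the level itself is a reported result, so the difference would be visible. Levels taken at a zero intercept would not match the crude percentages or the 14.2 to 17.0% of the earlier cohorts. The relative gap also widens as prevalence falls, so infectivity after dosing would look disproportionately low.

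**Working it through.** **Inputs.** From the Sample size section: 15% with ICC 0.5, 20% with ICC 0.4, 30% with ICC 0.8, 30 participants per group, 40 mosquitoes per participant and timepoint, an expected reduction of 90% tested against 80%, and one-sided 0.025. Assumptions: a normal random intercept u with SD s, and the ICC on the latent logistic scale, so s² = (π²/3) × ICC/(1 − ICC).

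**Step 1. The plan's own power, to see which ICC scale it implies.** A paired day 0 and day 5 random-intercept logistic model was simulated and fitted by maximum likelihood, with a Wald test against an 80% reduction. With the latent scale and 15% as the zero-intercept participant, power was 98.5% with the reduction as an odds ratio and 97.5% as a risk ratio (200 runs each), and 98.4% as an odds ratio in 800 runs. The stated figure is 97%. With the ICC read as a variance or an SD, power was 89 to 94%. With the latent scale and 15% as the population mean, it was 87 to 89%. The other two stated powers (91.5% and 96%) reproduce under some variants only. With 200 runs the Monte Carlo error is about 1 to 2 points. This favours the latent scale but does not prove it.

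**Step 2. Zero-intercept value against arm average.** Solve E[expit(a + u)] = p for a, with u ~ N(0, s²). The model then shows expit(a).

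| True average p | ICC | s² | a | Shown, expit(a) | Shown / true |
|---|---|---|---|---|---|
| 15% | 0.5 | 3.29 | −2.60 | 6.9% | 0.46 |
| 20% | 0.4 | 2.19 | −1.91 | 13.0% | 0.65 |
| 30% | 0.8 | 13.16 | −2.12 | 10.7% | 0.36 |

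After dosing, with the first row's odds multiplied by 0.1, the zero-intercept value is 0.73% against a true average of 2.84%, a ratio of 0.26.

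**Step 3. Sensitivity.**
- ICC read as a variance s² of 0.4 to 0.8, true average 15%: shown 13.4% to 12.0%, ratio 0.89 to 0.80.
- 15% taken as the zero-intercept participant, latent ICC 0.5: the true average is 24.4%, ratio 0.61.
- No ICC at all, solving for s from the earlier cohorts' two percentages and assuming 40 mosquitoes per person: s is 1.6 to 2.6, ratio 0.51 to 0.27.

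**Step 4. Does averaging close the gap?** In 600 simulated trials (true 15%, latent ICC 0.5) the mean day 0 estimates were 6.9% from the fixed effects, 14.6% after integrating over the intercept, and 14.9% crude. At day 5 they were 0.74%, 2.8% and 2.8%. In 400 trials with 27% of participants assumed never infectious, integration gave 18.7% against a crude 14.9%, and the fixed effects gave 7.4%. Integration over a normal intercept can therefore overshoot.

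**Step 5. Density.** With a log link, the zero-intercept mean divided by the arm mean is exp(−s²/2), so the reported mean is too low by a factor exp(s²/2). The SAP gives no log-scale variance. For illustration only, an assumed s² of 0.5 gives a ratio of 0.78, 1.39 gives 0.50, and 3.29 gives 0.19. The factor is the same in every arm and on every day under one random-intercept variance, so it cancels from density ratios.

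**The case against.** The strongest reply is that the fault is read into silence. The SAP nowhere says that the random intercept will be set to zero. Averaging predictions over participants uses the same models and fits the word average. The Statistical Principles section also says that binary data will be given as counts and proportions, so crude percentages may appear anyway. This stands in part: one cannot say that the reported levels will be wrong. But the SAP ties the estimated proportions and densities to these models, and fixed-effect prediction is the usual way to read levels from them. A plan should settle which is meant.

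The size is also open to challenge. The ICC scale is not stated. The 15% is given for the average participant, which may mean the zero-intercept person. The SAP itself describes both 0.5 and 0.8 as conservative. All of this stands and is why a range is given. The earlier cohorts' figures still point to large variation, although that calculation assumes a mosquito number.

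The reach is limited too. These outcomes answer secondary objectives, which the SAP treats as hypothesis-generating. The primary outcome, the reduction in DMFA at day 5, has its own log-link model and is not touched by this point.

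A reader might infer that the trial will publish averages less than half the true ones. The document does not support that. It requires a zero-intercept prediction, which is not stated, and a latent ICC near 0.5 or above. At ICC 0.4 and 20% the ratio is 0.65. A reader might also attach a fixed factor to the density understatement, but the SAP offers no variance from which to compute one.

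**Conclusion.** The concern holds in a limited form. The target is an arm average, the named tool is a random-intercept model, and the step between them is not fixed. If zero-intercept predictions are reported, prevalence will be understated. At the SAP's planning values on the latent scale the ratio of shown to true is 0.46, 0.65 and 0.36. It is 0.80 to 0.89 at 15% if the ICC is a variance, and 0.27 to 0.51 if calibrated to the earlier cohorts with 40 mosquitoes per person. Mean density would be too low by exp(variance/2), of unknown size.

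The comparisons survive. Density ratios are unchanged, and odds ratios remain valid as effects for a given participant. The results rest on a normal random intercept, and the prevalence figures also on the assumed ICC scale. The change is worth making before analysis because it is cheap and removes a possible two-fold ambiguity in reported levels, but it does not bear on the primary endpoint.

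**What to change.** In both sections, state that the per-arm, per-day proportions and densities are population-averaged, and name the method. Either of these would do:

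- GEE or another marginal model, with robust standard errors clustered on participant.
- Mixed-model predictions averaged over participants, with confidence intervals from a bootstrap that resamples participants.

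Report the crude percentages and crude mean densities alongside as a check. This matters most for the second option, because integration over a normal intercept can overshoot when many participants are never infectious. In the earlier cohorts 20.5 to 34.0% (100 minus 79.5 and 66.0) infected no mosquito at enrolment. Label the mixed-model odds ratios as participant-conditional.

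The cost is a few sentences in the SAP and one extra post-estimation step. No data collection or sample size changes.
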